## 4. STATISTICAL ANALYSES

### 4.1. General Considerations

Unless specified otherwise, efficacy data summaries will be provided by intervention group for the FAS. Data primarily will be summarized using descriptive statistics. Continuous variables will be summarized using the number of observations, mean, SD, median, interquartile range, minimum and maximum, as appropriate. Categorical values will be summarized using the number of observations and percentages as appropriate. In addition, graphical data displays (e.g., line plots) and participant listings may also be used to summarize/present the data.

For binary endpoints, treatment comparisons will be performed using a CMH test stratified by age group at screening (adolescents <18 years and adults  $\geq 18$  years), baseline weight category for adults (i.e.,  $\leq 90$ kg in adults,  $> 90$ kg in adults, adolescents) and geographic region (AMER, EU, and APAC) if applicable. A stratification factor may not be used if the sample size is small within that stratum among adolescents. In case of rare events for binary endpoints, Fisher's exact test will be used. For repeated measure continuous endpoints, treatment comparisons will be performed using a MMRM model. The MMRM will include treatment, age group, baseline weight, geographic region and baseline value, as explanatory factors. The MMRM model will also include visit, treatment group by visit interaction, and baseline value by visit interaction as additional explanatory factors. An unrestricted (UN) variance-covariance matrix for repeated measures within a participant will be used. If the model with unstructured covariance structure does not converge, alternative covariance structures will be tried in the following order, with the first structure that converges being used in the analysis: heterogeneous Toeplitz, standard Toeplitz, and autoregressive of order 1. The LS mean estimates and their corresponding 95% CIs will be provided at each timepoint. In addition, the estimates of LS mean difference and 95% CIs between treatment groups will be provided. Analysis of covariance (ANCOVA) will be used to analyze some continuous endpoints when appropriate. The ANCOVA will include treatment group, baseline value, baseline weight, geographic region and age group. The LS mean estimates and their corresponding 95% CI will be provided. In addition, LS mean difference and 95% CIs between treatment groups will be provided. For time to event endpoints during the randomized withdrawal period, treatment comparisons will be performed using a log-rank test. Life table estimates of cumulative rate by treatment group will be provided to evaluate the timing of event occurrence in different treatment groups.

In general, all statistical tests will be performed at a significance level of 0.05 (2-sided) unless otherwise specified. Multiplicity adjustment procedure will be used to control the overall Type I error rate for the primary and key secondary endpoints (section 2.1). No adjustments for multiple comparisons will be made for other secondary endpoints and exploratory endpoints. Nominal p-values for other secondary and exploratory endpoints will be reported but should not be used to infer statistical significance.

The baseline measurement for efficacy endpoints is defined as the closest measurement taken prior to or on the first study agent administration date. The baseline measurement for other endpoints

including safety, PK and immunogenicity is defined as the closest measurement taken prior to the time of the first study agent administration.

#### 4.1.1. Analysis Visit Windows

Unless otherwise specified, nominal visits will be used for all by visit analyses. The study visits scheduled after randomization should occur at the time delineated in the Schedule of Activities of the protocol.

#### 4.1.2. Reference Date, Study Day and Relative Day

The Reference Date is the date of the first study agent administration. If the date of the first study agent administration is missing or the first study agent administration is not done, then the Reference Date equals the corresponding visit date (e.g., Week 0 visit date). If the corresponding visit date is also missing, then the Reference Date equals the randomization date. Study day is defined as the number of days from the study reference date to the event/visit date. It will be calculated as follows:

- If the event/assessment occurs on or after the reference date, then study day = event/assessment date – reference date + 1.
- If the event/assessment occurs before the reference date, then study day = event/assessment date – reference date.

Hence, the day of reference date is Study Day 1; the previous day is Study Day -1.

#### 4.1.3. Change and Percent Change From Baseline

The change and percent change from baseline are calculated using the formula:

$$\text{Change} = \text{Post Baseline Value} - \text{Baseline Value}$$
$$\text{Percent change} = \frac{(\text{Post Baseline Value} - \text{Baseline Value})}{\text{Baseline Value}} \times 100$$

If a higher score indicates more severe disease in efficacy assessments, then a negative change indicates an improvement, and a positive change indicates worsening.

### 4.2. Co-Primary Endpoints/Estimands Analysis

#### 4.2.1. Definition of Endpoints

The following co-primary efficacy endpoints are defined in the variable attribute of the co-primary estimands 1a and 1b.

- Achieving PASI 90 response at Week 16
- Achieving IGA 0 or 1 response at Week 16

#### 4.2.1.1. Psoriasis Area and Severity Index (PASI)

The PASI is a system used for assessing and grading the severity of psoriatic lesions and their response to therapy. In the PASI system, the body is divided into 4 regions: the head, trunk, upper extremities, and lower extremities which account for 10%, 30%, 20%, and 40% of the total BSA, respectively. Each of these areas is assessed separately for erythema, induration, and scaling, which are each rated on a scale of 0 to 4; and the area of involvement for psoriatic lesion is rated on a scale of 0 (no involvement) to 6 (90% to 100% involvement). The PASI produces a numeric score that can range from 0 (no psoriasis) to 72. A higher score indicates more severe disease.

Meeting the PASI 90 criteria: defined as having at least a 90% improvement from baseline in PASI total score.

#### 4.2.1.2. Investigator's Global Assessment (IGA)

The IGA documents the physician's assessment of the participant's psoriasis status according to the following categories: induration, scaling, and erythema. The participant's psoriasis is assessed as cleared (0), minimal (1), mild (2), moderate (3), or severe (4).

Meeting the IGA 0 or 1 criteria: defined as achieving an IGA score of cleared (0) or minimal (1), AND at least a 2-grade improvement from baseline.

#### 4.2.2. Estimands

**Primary Study Objective:** To evaluate the efficacy of JNJ-77242113 compared to placebo at Week 16 in participants with moderate to severe plaque psoriasis.

##### **Clinical Questions of Interest:**

For an adult or adolescent patient with moderate to severe psoriasis, what would be the expected effect of being assigned JNJ-77242113 on the likelihood of experiencing a treatment response at Week 16?

#### 4.2.2.1. Co-Primary Estimands (1a and 1b)

The co-primary estimands, aligned with the above primary objective and clinical question of interest, provide precise descriptions of the treatment effect of interest that are defined by the following 5 attributes. Both co-primary estimands have the same attributes, except for the variable definition that corresponds to each co-primary endpoint.

##### 4.2.2.1.1. Co-Primary Estimand 1a

##### **Treatment condition of interest vs Alternative treatment condition:**

- Experimental: JNJ-77242113 200 mg QD
- Placebo

**Population:** Patients  $\geq 12$  years of age with moderate to severe plaque psoriasis

**Variable:** Achieving a PASI 90 response at Week 16, where a PASI 90 responder is defined as a patient meeting the PASI 90 criteria at Week 16 and not experiencing either ICE 1 or 2.

**Intercurrent Events (ICEs) and Corresponding Strategies (Refer to Table 2):**

**Table 2: ICEs and Their Corresponding Strategies**

ICEs	Strategy for Addressing Intercurrent Events
1. Discontinuation of treatment due to lack of efficacy, or due to an AE of worsening of psoriasis. 2. Initiation of other medication or therapy that could improve psoriasis (see Appendix 6.7).	Composite Strategy: The occurrence of these ICEs is captured in the variable definition as patients with these ICEs are considered non-responders.
3. Discontinuation of treatment for other reasons than ICE 1	Treatment Policy: Strategy targeting the effect of treatment assignment, regardless of the occurrence of this ICE.

Note: For patients experiencing multiple ICEs, ICE 2 will override ICE 3 and the composite strategy will be applied.

**Population Level Summary:** Difference in proportions between JNJ-77242113 and placebo.

#### 4.2.2.1.2. Co-Primary Estimand 1b

The estimand 1b has the same attributes as in Estimand 1a, except for the variable definition:

Achieving an IGA 0 or 1 response at Week 16, where an IGA 0 or 1 responder is defined as a patient meeting the IGA 0 or 1 criteria at Week 16 and not experiencing either ICE 1 or 2.

#### 4.2.2.2. Supplementary Estimands Sup1a and Sup1b (Treatment Policy Estimands):

In these supplementary estimands, the components that change from the definition of the co-primary estimands are:

**Variable:** Achieving a response at Week 16 based on a scale will be the same as meeting the defined efficacy criteria, without accounting for ICEs 1 and 2 in the response definition.

**Treatment Policy Strategy:** Strategy targeting the effect of treatment assignment, regardless of the occurrence of ICEs.

### 4.2.3. Analysis Methods

#### 4.2.3.1. Main Analytical Approach

Analysis for the co-primary endpoints will be based on FAS, including data from all randomized participants. Participants will be analyzed based on their assigned intervention group, regardless of the actual intervention received.

According to the co-primary estimands 1a and 1b, participants with ICEs 1-2 before Week 16 will be considered as non-responders in co-primary endpoints at Week 16. For participants with ICE

3, observed data after this ICE will be utilized in the analysis. For participants experiencing multiple ICEs, an ICE2 will override an ICE 3. After accounting for the ICEs for the primary estimands, participants with missing value for the co-primary endpoints at Week 16 will be considered as non-responders.

In the primary analyses, the proportion of PASI 90 responders and IGA 0 or 1 responders at Week 16 will be summarized by treatment group. To address the primary objective, a 2-sided ( $\alpha=0.05$ ) CMH chi-square test stratified by age group (adults, adolescents), baseline weight category for adults ( $\leq 90$ kg in adults,  $>90$ kg in adults, adolescents), and geographic region (AMER, EU, APAC) will be used.

Difference in response rates between the JNJ-77242113 group and the placebo group at Week 16 and their corresponding 95% CIs (using Miettinen-Nurminen method [[REFERENCES](#)]) will be calculated adjusting for age group, baseline weight category for adults, and geographic region using Mantel-Haenszel (MH) weights.

The study will be considered positive if the JNJ-77242113 group is significantly different from the placebo group for both co-primary endpoints. Both co-primary endpoints will be tested at a 2-sided  $\alpha$  level of 0.05. If at least one of the comparisons is not significant at the 2-sided  $\alpha$  level of 0.05, the co-primary endpoints will be considered not significant.

In addition, the proportion of PASI 90 responders and IGA 0 or 1 responders at Week 16 will be summarized by region, country, and investigator site. The coprimary endpoints will also be summarized and compared between treatment group among adolescent participants. To evaluate the consistency of the efficacy, subgroup analyses of the co-primary endpoints based on demographics, baseline disease characteristics and previous psoriasis medications and therapies will be performed. The detailed subgroup analyses for the coprimary endpoints are specified in Section 4.6.6.

#### **4.2.3.2. Sensitivity Analyses**

To address the robustness of the primary endpoint analysis results, two sensitivity analyses will be performed to assess missing data assumptions.

##### **4.2.3.2.1. Sensitivity Analysis 1**

Under the co-primary estimands, a sensitivity analysis using multiple imputation will be performed for each co-primary endpoint. After accounting for the ICEs, missing data will be imputed using multiple imputations (MI) by fully conditional specification (FCS).

More specifically, the missing PASI 90 response and IGA 0 or 1 response will be imputed with FCS logistic regression including treatment group, baseline PASI score or IGA score, PASI 90 response or IGA 0 or 1 response status through Week 16, age group, baseline weight category for adults, and geographic region in the model with seed = 789 and 500 imputations.

A CMH test stratified by age group, baseline weight category for adults, and geographic region will be used to obtain the CMH statistic for each imputed dataset.

The general association test statistic from the CMH test for each imputed dataset will be transformed using the Wilson-Hilferty transformation ([Wilson and Hilferty, 1931](#)) to create a more normal distributed statistic:

$$Z = \frac{(CMH)^{(1/3)} - 7/9}{(2/9)^{(1/2)}}.$$

The resulting transformed values will be combined using SAS PROC MIANALYZE to obtain an overall p-value for the CMH test.

The common risk differences and 95% CIs in co-primary endpoints will be calculated using Mantel-Haenszel stratum weights and Sato variance estimator ([Sato, 1989](#)) adjusting for age group, baseline weight category for adults, and geographic region for each imputed dataset. The resulting values will be combined to obtain an overall risk difference and 95% CI.

#### 4.2.3.2.2. Sensitivity Analysis 2

Under the co-primary estimands, another sensitivity analysis will be performed using a tipping point analysis with Bernoulli draws to impute missing PASI 90 and IGA 0 or 1 response status at Week 16 after ICEs are accounted for. The tipping point analysis involves the following distinct steps:

1. Some p will be assumed for each treatment group's response rate, which could vary by treatment group, to impute the response status (Yes/No) for participants with a missing response based on a Bernoulli distribution. This will be repeated 200 times with seed = 20240719 to generate 200 multiple imputations.
2. The common risk difference between JNJ-77242113 and placebo will be calculated using Mantel-Haenszel stratum weights adjusting for age group, baseline weight category for adults, and geographic region for each imputed dataset. The resulting values will be combined to obtain an overall risk difference.
3. The results (with a Wilson-Hilferty transformation) from the imputed data sets will then be combined to produce p-value based on Rubin's rule.

The analysis will be repeated for a range of values for p (for example, 0% to 100% in increments of 10%, for the placebo group and the JNJ-77242113 group independently). For this tipping point analysis, the analysis will allow for assumptions about the response rates in the two arms to vary independently; furthermore, it will include scenarios where imputed missing values on JNJ-77242113 group have worse outcomes than missing values on the placebo group.

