- The proportions of participants who experienced 1 or more AEs were similar in the combined JNJ-77242113 (52.4%) and placebo (51.2%) groups.
- The most frequently reported AEs were in the Infections and infestations SOC and were similar between the combined JNJ-77242113 (30.2%) and placebo (27.9%) groups. The most common AEs by PT in this SOC were COVID-19 (10.8% and 11.6%), nasopharyngitis (7.1% and 4.7%), and upper respiratory tract infection (2.4% and 2.3%) in the combined JNJ-77242113 and placebo groups, respectively. In the Gastrointestinal disorders SOC, AEs were reported in 11.3% of participants in the combined JNJ-77242113 group and 11.6% in the placebo group. Other AEs by PT reported by at least 5% of participants included headache and cough.
- The percentage of participants with one or more SAEs through the end of study was small, with 3 participants (1.4%) experiencing one SAE each. All events were singular in nature and deemed not related to study intervention per the investigator.
- The proportion of participants who discontinued study intervention due to 1 or more AEs was small ($n=6$). Three out of the six events were in the Gastrointestinal SOC ($n=1$ each: abdominal pain, abdominal discomfort, and nausea). The other three events included suicide attempt, weight increase, and transaminases increase ($n=1$ each).
- Rates of abnormal labs were generally low and comparable between the treatment groups.
- There were no deaths or malignancies reported.

Human Pharmacokinetics and Immunogenicity

The clinical data available to date supporting the safety, PK and PD of JNJ-77242113 are from completed Phase 1 studies in healthy subjects and Phase 2 studies in adults with moderate to severe plaque psoriasis.

PK data from FIH study PN-235-01 indicate that systemic exposure (C_{max} and AUC) to JNJ-77242113 is dose proportional across the dose range evaluated to date. After multiple once daily dosing, steady state was achieved by Day 7 (earliest timepoint evaluated), with minimal drug accumulation consistent with the observed mean terminal phase half-life of approximately 9 to 12 hours.

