- Removed hypothetical estimand for the co-primary endpoints and key secondary endpoints.
- Added two sensitivity analyses (one using multiple imputation and one using tipping point analysis) to the primary estimands for the co-primary endpoints.
- Added subgroup analysis based on ethnicity (Hispanic/Latino or Not Hispanic/Latino, Not Reported, and Unknown).

In addition, the following modifications were also made:

- Clarified the definition of baseline.
- Clarified when an adverse event is considered treatment emergent by adding a 4-week window after last dose or treatment discontinuation when evaluating safety for the 200 mg QD regimen. The same 4-week window rule applies to lab, vital sign and ECG data analyses.
- Clarified the calculations for PSSD symptom score and sign score.
- Clarified ECG analyses.
- Removed GenPs-SFQ analysis from Week 64 through Week 156.
- Noted that multiplicity adjusted p-values will be provided.
- Added safety summary through Week 52.
- Minor grammatical, formatting, or spelling changes were made.

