## 5. SAMPLE SIZE DETERMINATION

This study is designed to evaluate the efficacy of JNJ-77242113 versus placebo and to evaluate the maintenance of response for JNJ-77242113. The sample size was also chosen to ensure a reasonable safety database to assess the overall safety of JNJ-77242113. These study objectives were taken into consideration in determining the sample size.

The assumptions for the sample size and power calculations were based on placebo response rates from the historical psoriasis clinical studies and data from the JNJ-77242113 Phase 2b Study 77242113PSO2001.

- The proportion of participants in the placebo group who achieve an IGA score of cleared (0) or minimal (1) and at least a 2-grade improvement from baseline and a PASI 90 response at Week 16 are 8% and 5%, respectively.
- The proportion of participants in the JNJ-77242113 group who achieve an IGA score of cleared (0) or minimal (1) at least a 2-grade improvement from baseline and a PASI 90 response at Week 16 are 64% and 59%, respectively.

Based on the above assumptions, a total of approximately 600 participants to be randomized in a 2:1 ratio to JNJ-77242113 200 mg once daily (n=400) or placebo (n=200) at Week 0 will provide >99% power to detect significant differences at a 2-sided significance level of 0.05 for both co-primary endpoints in the proportion of participants achieving an IGA score of cleared (0) or minimal (1) and the proportion of participants who achieve a PASI 90 response between the placebo and JNJ-77242113 groups at Week 16.

In addition, assuming approximately 75% of the adult participants originally randomized to JNJ-77242113 group are PASI 75 responders and will be randomized in a 1:1 ratio to either continue receiving JNJ-77242113 or undergoing withdrawal of JNJ-77242113 at Week 24. This portion of the study will ensure at least 95% power to detect a 20 percentage points of difference in PASI 75 response rates at Week 52 between these 2 groups.

[Table 9](#) provides the power for detecting a treatment difference under varying assumptions for the primary and selected key secondary endpoints.

**Table 9: Power to Detect a Treatment Effect Based on Different Proportions of Participants Achieving the Co-primary Endpoints at Week 16 and PASI 75 at Week 52**

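### Sensitivity Analysis 1 has no on/off-treatment term, so Week 16 values missing after ICE 3 lean toward a continued-treatment outcome that fits the treatment-policy strategy poorly

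*SAP*

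**What the plan says.** SAP Table 2 assigns ICEs 1 and 2 to a composite strategy (non-response). ICE 3, stopping treatment for any reason other than ICE 1, is assigned to treatment policy: "Strategy targeting the effect of treatment assignment, regardless of the occurrence of this ICE".

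The plan handles Week 16 data as follows:

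- **Main analysis (SAP 4.2.3.1).** Data observed after ICE 3 are used. Any Week 16 value still missing counts as non-response.
- **Follow-up (Protocol 7.1).** Participants who stop treatment but stay in the study keep attending visits, so Week 16 data after stopping can exist.
- **Sensitivity Analysis 1 (SAP 4.2.3.2.1).** It is declared under the co-primary estimands: "After accounting for the ICEs, missing data will be imputed using multiple imputations (MI) by fully conditional specification (FCS". The logistic model contains treatment group, baseline PASI or IGA score, response status through Week 16, age group, adult weight category and region. It contains nothing on discontinuation or ICE 3, and there is no separate off-treatment model or reference-based rule.
- **Sensitivity Analysis 2 (SAP 4.2.3.2.2).** This tipping-point analysis assigns each arm its own response rate for missing values. The example grid runs from 0% to 100% in steps of 10, and the scenarios include worse outcomes on active than on placebo.

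**The concern.** Under treatment policy, the target for someone who stopped JNJ-77242113 and has no Week 16 value is the response actually reached after stopping. The model in Sensitivity Analysis 1 cannot tell that person from someone in the same arm with the same history who is still taking the tablets. Most of the arm will be on treatment, so the prediction comes mainly from on-treatment outcomes. The last recorded response may itself date from before stopping.

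The lean is likely to be one-sided, because placebo participants who stop lose no active treatment. The practical risk is one of interpretation: a result more favourable than the non-responder analysis could be read as showing that the primary analysis is conservative, when part of the gain comes from this assumption.

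**Working it through.** **1. Planning figures.** SAP section 5 plans a "2:1 ratio to JNJ-77242113 200 mg once daily (n=400) or placebo (n=200) at Week 0" and "a 2-sided significance level of 0.05 for both co-primary endpoints". Assumed rates are 8% against 64% for IGA 0/1 and 5% against 59% for PASI 90. A two-proportion power calculation with 200 and 400 participants gives more than 99.9% for every co-primary row of Table 9, as stated. The planned differences are 64 − 8 = 56 points and 59 − 5 = 54 points.

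**2. Who is imputed.** Four groups of participants need separating:

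- ICE 1 or 2: non-responder, not imputed.
- ICE 3 with Week 16 observed: real off-treatment value, not imputed.
- On treatment with Week 16 missing: imputed, and the model suits them.
- ICE 3 with Week 16 missing: imputed from a model with no off-treatment term. Only this group is at issue.

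**3. Upper bound.** Let m be the share of the active arm in that last group, p_on the rate at which they would be imputed if treated as fully on treatment, and p_off their true rate.

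Overstatement = m × (p_on − p_off)

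The documents give neither m nor p_off. I assume m of 3%, 6% and 10%, and p_off from the planned placebo rate up to 30%.

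| m | PASI 90: m × (59 − 30) to m × (59 − 5) | IGA 0/1: m × (64 − 30) to m × (64 − 8) |
|---|---|---|
| 3% | 0.9 to 1.6 points | 1.0 to 1.7 points |
| 6% | 1.7 to 3.2 points | 2.0 to 3.4 points |
| 10% | 2.9 to 5.4 points | 3.4 to 5.6 points |

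These are upper bounds for the assumed inputs, because they put the imputed value at the full on-treatment rate.

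**4. Allowing for response history and retrieved data.** An illustrative simulation used a simplified single-model imputation. It assumed 8% ICE 3 in the active arm, true off-treatment response of 8%, on-treatment response of about 59%, and Week 12 response of 50% on treatment and 25% in those who stopped.

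- Without Week 12 response in the model and with no retrieved data, missing values were imputed at 59.1%. The difference was 54.0 against a true 49.9, an excess of 4.1 points. The formula in step 3 gives 8% × (59 − 8) = 4.1.
- With Week 12 response in the model and no retrieved data, they were imputed at 42.1%. The difference was 52.2 against 49.5, an excess of 2.7 points.
- With Week 12 response and 75% of stoppers observed at Week 16, they were imputed at 43.1%. The difference was 50.6 against 50.0, an excess of 0.6 points.

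So 42% to 43% is well below the on-treatment rate, but also far above the assumed truth of 8%.

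**5. Consequence for the conclusion.** Take the largest case, 10% missing and imputed at the placebo rate instead. The IGA 0/1 difference falls from 56.0 to 50.4 points and the PASI 90 difference from 54.0 to 48.6. Power stays above 99.9%.

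**The case against.** The strongest reply is that this is a debatable missing-at-random assumption for a small subset, in an analysis whose stated purpose is to vary missing-data assumptions. Much of that stands. Observed values after ICE 3 are used, the model is fitted to all observed data in the arm including retrieved off-treatment values, and response status may include visits after stopping. The imputed value is a mixture. Nothing confirmatory rests on it: the main analysis counts these participants as non-responders, and tipping-point rates of 0% to 30% on active already span the off-treatment range assumed above.

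The size is also open to challenge. A reader might infer from the "mean terminal phase half-life of approximately 9 to 12 hours" (Protocol 2.2) that response falls quickly to the placebo level after stopping. That is a plasma half-life, not a rate of loss of skin response. SAP Table 9 itself assumes that 60% to 70% of the withdrawal group are PASI 75 responders at Week 52, against 80% to 90% on continued treatment. Those planning values concern Week 24 PASI 75 responders and do not transfer directly to early stoppers or to PASI 90. As an illustration only, the ratios 60/80 and 70/90 applied to 59% give an off-treatment rate of about 44% to 46%. The upper bound is then about 0.4, 0.8 to 0.9 and 1.3 to 1.5 points at 3%, 6% and 10% missing.

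The missingness inputs have little support either. The nearest figure is six AE discontinuations among 255 adults in the Phase 2b study (6/255 = 2.4%), which leaves out other reasons for stopping.

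These arguments limit the size of the mismatch but do not remove it. The tipping-point analysis applies one rate per arm to all missing values, so it does not separate those missing after ICE 3 from those missing on treatment, and the SAP does not comment on the assumption.

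**Conclusion.** The point holds in a limited form. Sensitivity Analysis 1 is declared under estimands that use treatment policy for ICE 3, yet its imputation ignores treatment status. For values missing after ICE 3 it leans toward a continued-treatment outcome, probably in favour of JNJ-77242113. The overstatement is at most 0.9 to 5.6 points across the assumed 3% to 10% missing and the assumed off-treatment rates. It was 0.6 to 2.7 points in the simulation with response history in the model. All of these rest on assumed inputs.

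Two stronger readings are not supported:

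- A reader might infer that the analysis treats stoppers as if still on drug and so targets a hypothetical estimand, particularly since the SAP's Summary of Changes says "Removed hypothetical estimand for the co-primary endpoints and key secondary endpoints". The declared estimand does not change and the imputed values are a mixture. The same summary lists this multiple-imputation analysis among the changes made on regulatory comments.
- A reader might infer that the trial's evidence is weakened. The primary analysis and the tipping-point analysis do not rely on this assumption, and power and the significance conclusion are unaffected.

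Only the estimate from Sensitivity Analysis 1 and its interpretation are at stake. This is a cheap improvement of low to moderate priority.

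**What to change.** In SAP 4.2.3.2.1:

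- Add an off-treatment (ICE 3) indicator to the imputation model, by arm where data allow, so that values missing after ICE 3 draw on participants observed at Week 16 after stopping.
- Pre-specify a fallback if such data are too sparse to fit. Reference-based imputation, or the primary non-responder rule for those participants, would serve. Each carries its own assumption, and both the choice and the sparseness threshold are the sponsor's to justify.
- Keep the present model for participants missing while on treatment.

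If the model is left unchanged, the SAP should at least state that it assumes missing at random regardless of treatment status. SAP 4.4.2.4 reuses this method from Week 64 to Week 156, so it should say whether the change carries over.

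The cost is SAP wording and modest programming, somewhat wider intervals when few off-treatment values are retrieved, and a slightly less favourable sensitivity estimate.
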